7.0 SUBJECT EVALUATION

7.1 Evaluations

7.1.1 Home-based Data Collection

- 1) **Anthropometrics** will include self-reported height and weight.
- 2) **Nutrition and physical activity knowledge and preferences** will be measured using questions adapted from a battery of questions developed and validated by our team (The Preferences and Self-Efficacy of Diet and Physical Activity Behaviors Questionnaires for Latinas) (preparing manuscript for submission).
- 3) **Patient-reported psychosocial/Quality of Life outcomes** will be measured via questionnaires assessing self-efficacy and motivation to make dietary and physical activity changes ¹⁶⁻¹⁹, stress (Hispanic Stress Inventory)²⁰, and quality of life (PROMIS 10).²¹

7.1.2 Retention calls and data collection

- 1) During monthly retention call participants will be asked about use of and technical issues with their study Fitbits. These data will be recorded to understand Fitbit usage patterns.
- 2) During monthly retention call, participants will be asked about COVID-19 symptoms, testing and isolation. These data will be used to examine the effects of the COVID-19 pandemic on intervention adherence patterns.

8.0 SUBJECT DISCONTINUATION OF ACTIVE TREATMENT- WITHDRAWL

Participants can discontinue participating at any time and for any reason.

9.0 CONCOMITANT MEDICATIONS

Participants will be asked during the Baseline 1 questionnaire about comorbidities and medication use.

10.0 ADVERSE EVENTS

10.1 Adverse Event

This is a low risk study with no intervention agent. We do encourage participants to be physically active to be able to capture, and compare, physical activity levels across devices. Any adverse events will be recorded in the Adverse Event Summary From (**Appendix I**) and reported as follows.

10.2 Serious Adverse Event

Adverse event grading scale:

0= No Adverse Event or within normal limits

1= Mild Severity: Transient laboratory test alterations; discomforts noted but no disruption of daily activities; no therapy, or only symptomatic therapy required

2= Moderate Severity: Laboratory test alterations indicating injury without long-term risk; discomfort sufficient to modify normal daily activity; specific therapy required (i.e., more than symptomatic)

3= Serious Severity: Laboratory test indicating a serious health threat or permanent injury; incapacity, inability to work, inability to perform normal daily activity; hospitalization required or prolonged; emergency treatment required; life-threatening events; death.

Plan for unanticipated AE reporting: All unanticipated AEs related to the study procedures that are severe or serious will be reported by [name] to the IRB within 7 days of notification of the investigator.

Plan for anticipated AE reporting: All serious anticipated AEs related to the study procedures will be reported by [name] to the IRB within 7 days of notification of the investigator.

Plan for ongoing review of results: The PIs will be notified within 24 hours by the research manager of any early terminations due to an adverse event.

Plan for safety review: The PI will perform a cumulative review of all adverse events and premature terminations review every 6 months after study initiation or after completion of 50% of participant visits, whichever occurs first.

Plan for annual reporting: A summary of the investigation including all adverse events and how they were handled, enrollment, drop-outs and reason for discontinuation and any protocol modifications will be provided to the IRB on an annual basis.

Annual Reports will contain:

- a. The number of adverse events and an explanation of how each event was handled
- b. The number of complaints and how each complaint was handled
- c. The number of subject withdrawals and an explanation of why the subject withdrew or was withdrawn
- d. The number of protocol deviations and how each was handled

The occurrence of any serious and unexpected event may prompt changes in study protocol. Any such change will be approved by the IRB before implementation.

11.0 DATA AND SAFETY MONITORING PLAN

A data safety and monitoring committee is not needed as this is not a Phase 3 clinical trial. Drs. [name] and [name] will oversee the data safety and monitoring for this project. They will meet with the study staff to discuss protocols and procedures to ensure participant safety and the validity and integrity of the study data. All staff members will attend trainings on these procedures and will be given information on the importance of reporting any adverse event immediately. Drs. [name], [name] and the Institutional Review Office (IRO) will be alerted about any adverse events immediately. Drs. [name] and [name] will discuss any adverse effects and examine available data to assess whether safety is compromised. Action to resolve the adverse event will be discussed with IRO prior to implementation. The team will enact any actions recommended by the IRO.

12.0 DATA ENTRY AND MANAGEMENT/CONFIDENTIALITY

Collaborative Data Services (CDS) Shared Resource. CDS will use REDCap (Research Electronic Data Capture) to track, collect and maintain study data. REDCap is a web-based research-centric electronic data capture system supported through a federally-funded consortium led by Vanderbilt University. The system is fully supported by CDS, which maintains the REDCap installation and provides a secure system with high reliability and availability. CDS will design, build, and maintain the REDCap data forms that will be used for data capture, including

screening, participant questionnaires, and staff forms for participant tracking. CDS will provide programming extensions to REDCap when necessary to improve efficiency.

Specific to this study, CDS will build an automated bi-directional text message interface where participants will report their nutrition and physical activity goals and accomplishments, and the REDCap system will send automated motivational responses as provided by the study team. However, CDS will not monitor participant responses. All bidirectional communication with participants will take place with designated Spanish-speaking research staff only overseen by [name]. CDS will also build an integrated messaging system to send appointment reminders via email or text messaging (based on the participant's choice) that will be used to improve participant retention rates. CDS will also generate study tracking reports for staff to monitor day-to-day study activities. All staff have received Human Subject Research and HIPAA training. All data will be stored in a secure password protected computer folder, which only authorized research staff will have access to.

Fitbit Data

Fitbit PA data will be downloaded from Fitbit.com in weekly intervals up until their final follow-up visit. The data will reside on a server managed by the Fred Hutch IT group. Fred Hutch shared resource will develop a program to fetch and monitor PA data collected by Fitbit. Fitbit syncs user data through its smart phone application periodically and stores these data on their server. Fitbit Inc. offers an application-programming interface (API) for batch data access (<https://dev.Fitbit.com/docs>). The application is registered with Fitbit Inc., which grants a license to fetch data with the participants' consent. The program will collect the following data via the Fitbit API: steps, distance, calories and active times. The license allows the retrieval of both interday and intraday data (at one-minute level) on these activities. Participant data will be combined into a single data file for analyses. To monitor participant activity and Fitbit use, embedded within the program there are several visualizations of time-series activity history, and summary statistics for each participant. The program is written in R programming language and can run on a personal computer or a server. It is only on Fred Hutch's secure computing and networking environment where data collected by Fitbit, Inc. will be linked to the participants' questionnaire data responses. Neither questionnaire data will not be shared with Fitbit, Inc. nor will the link between the Fitbit.com username and subject name be shared anyone not authorized to work on this research study. [name] research team has successfully implemented this methodology in previous studies.

Text message management: The REDCap platform is a web-based software application that allows scientists to easily integrate and manage integration of SMS/text messaging into their research projects. Seattle-based study staff will manage and implement the REDCap platform. No personal health information will be transferred via the text-management system.

Participant ID's and personal telephone numbers are entered into a password protected web-based application (REDCap). REDCap requires strong passwords and will be accessed an encrypted (SSL) network connection only which is granted only to study personnel and software engineering staff that are trained in HIPAA compliance. Once participants are entered into the system, study personnel assign a start date and message suite to deliver to study participants. Participants then receive SMS messages according to the schedule defined for the message suite that they are assigned to (English or Spanish).

Participants can respond via SMS message to received messages. All SMS messages to participants will come from a single study phone number. This number is rented from Twilio, Inc. (see <twilio.com>). SMS messages originate from REDCap, which contacts Twilio's secure servers over an encrypted connection and then Twilio provides the gateway service to actually send the text messages. If participants reply to messages, they go to

Twilio and then Twilio's servers contact our servers to deliver the message back to our web application. Twilio does not store any of these text messages beyond the time it takes to pass them off to our web application. Twilio has access only to the phone number and the message.

REDCap includes functionality to notify study personnel of incoming SMS messages so that study personnel can then monitor and respond back to study participants via SMS message from within the web application. REDCap displays a conversation view of all messages per participant, both incoming and sent to the study team in a reverse time-based sorted order.

Using the Fitbit: The Fitbit device can be worn continuously for about 6 months before requiring a new battery. The Fitbit can be safely worn at all times, except when bathing or swimming. Participants will be required to sync data with the Fitbit web-based data repository at least once a week during the study period by simply opening the Fitbit app on their smartphone or signing onto their computer that has the program installed. Adherence to this requirement will be assessed each week by the study staff by logging into an online platform that tracks all Fitbit activity. The platform is described more thoroughly in the Data Management plan and Statistical Analysis.

Each participant will be assigned a de-identified anonymous user profile for Fitbit data collection. User profile emails will be an anonymous Gmail account that will be created for each participant by using the "+" tag in Gmail, in order to create multiple email accounts linked to one study account. User profile names will be participant's study IDs. *Note that the personal emails required for this study are only for emailing newsletters and not for the Fitbit user profiles.* The only personal information used to create the Fitbit accounts is a participant's height, weight, gender, and age. These data are essential in determining user-specific activity calculations, such as calories burned. Anyone who purchases the Fitbit for personal use, whether or not for research, would need to input this information to properly use the device.

During the course of the study participants will be instructed to wear the device while awake on their wrist and go about their normal daily routines and to remove when sleeping. Participants will be trained to sync their Fitbits using a computer or smartphone. The following types of data-points, in minute and per day units, will be collected daily and provided at the conclusion of the study by Fitbit:

- Number of steps walked
- Calories burned
- Distance walked
- Active minutes

Website: Text messages will direct study participants to the Spanish-language version of the Cook for Your Life website (www.cookforyourlife.org) (also available in English). Text messages will contain a unique de-identified URL tracking identifier and Google analytics will be used to track click through rates for each participant. The website will include study-specific web pages that participants will access via a unique login using their personal email address and a unique password. The study-specific web pages will include archived Zoom sessions, intervention materials, and community resources. These pages will be updated as the study progresses. Participants will have access to the study-specific web pages for 12 months following completion of the study. Participants randomized to the low dose study group will receive access to an archive of previously recorded sessions after completing 3-month follow-up.

In addition, Google analytics will be used to track overall usage of the website by study participants as a group by directing participants to enter the site with a private homepage that is available only to participants. Using

this method, it is not possible to track participants at an individual level, thus identifying information will not be collected, including IP addresses. The only extrapolation that can be made is whether or not a website user is a study participant based on their entry point to the site.

Google analytics provides the following information that can be used as measures of:

- Behavior (pages looked at, time on site, user pathways)
- Acquisition (where the audience is coming from social media, Google search, newsletters or otherwise)
- Conversions (goals to see if our users complete them, i.e., playing a video, downloading recipes or reading an article).
- Note: A HIPAA compliant server is not needed for the Cook for Your Life website because only participant IDs, and not PHI, will be used to track participants.

Post Intervention Data Collection. At 3 months, baseline data assessments will be repeated, including assessments at-home, web- and telephone-based. Participants Fitbit accounts will also be changed to participants own personal accounts and we will not maintain record of this account information and no longer have access to track Fitbit activity.

13.0 STATISTICAL CONSIDERATIONS

13.1 Study Design

This is a single-arm feasibility assessment.

13.2 Primary/Secondary Endpoints/Hypotheses and Analytical Methods

The endpoints for Aim 1, feasibility of intervention strategies, include accrual rate, adherence, retention, and acceptability (exit interview). Adherence will be measured by attendance to online sessions, text message responses, and use of the website. Retention will be measured by completion of all study assessments.

Acceptability will be measured on a Likert scale in each of a series of questions regarding various aspects of the trial during the exit interview. All endpoints will be summarized using descriptive statistics. Statistical differences in retention rates for each study assessment between study arms will be assessed by Chi-square tests, and acceptability by t-test of median per-patient scores.

Exploratory endpoints include changes in anthropometrics, mediators of behavior change, and patient-reported psychosocial/quality of life outcomes. Descriptive analyses will be conducted to summarize exploratory outcomes.

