FRED HUTCHINSON CANCER RESEARCH CENTER

Current version: 10/18/2021

Version	1	7/24/2019
Version	2	2/27/2020
Version	3	09/10/2020
Version	4	04/20/2021
Version	5	09/21/2021
Version	6	10/18/2021

Title of Protocol:
Adaptation and Evaluation of an Online and eHealth Diet and Physical Activity Program to Improve Cardiometabolic Health in Rural Latino Adults "Mi Vida Saludable en el Valle"

Investigator List:		
[name]	Associate Professor, Fred Hutch	[contact]
Co-Investigators:		
[name], ND, PhD	Associate Professor, Fred Hutch	[contact]
Biostatistician:		
[name]	Professor, Fred Hutch	[contact]

SPONSOR: CCSG Pilot Funds (May 1, 2019 - December 31, 2021)

Additional Performance Sites:		
Site	Investigator	Phone Number
Center for Community Health Promotion	[name]	[contact]

Emergency (24-hour) phone number: office [contact], [contact]

PROTOCOL SYNOPSIS

Protocol Title	Adaptation and Evaluation of an In-person and eHealth Diet and Physical Activity Program to Improve Cardiometabolic Health in Rural Latino Adults “Mi Vida Saludable en el Valle”
Protocol Number	RG1005660
Protocol Sponsor	CCSG
Trial Phase	Phase 2
Trial Type	Pilot RCT
Clinical Indication	Latino adults with history of hypertension, diabetes, cardiovascular disease, cancer, or obesity
Study Objectives	
Aim 1 Assess feasibility of a remotely delivered and remotely assessed online group sessions and eHealth communication intervention strategies as measured by quantitative (accrual rate, intervention adherence, study retention, percent data collection processes completed, duration of staff assistance to complete data collection) and qualitative (exit interviews) data. Feasibility of intervention delivery for staff within the rural community context will be assessed and necessary adaptations from the urban intervention delivery process will be documented.
 
Aim 2 Examine changes from baseline to 3 months in nutrition and physical activity knowledge and preferences, and changes in physical activity patterns as assessed via Fitbit data.

Study Design	Feasibility study
Population	Latino residents of the Lower Yakima Valley with a history of hypertension, diabetes, cardiovascular disease, cancer, and/or obesity.
Primary Endpoints	Accrual rate, intervention adherence, study retention, data completion rates, assessability/acceptability (exit interview) and required intervention delivery adaptations.

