In October 2021, investigation into the reason for slow recruitment (n=22 to date) revealed a high burden of data collection for potential participants. In addition, preliminary analyses of data currently being collected by [name] in a similar intervention among a predominantly non-Hispanic white population of urban breast cancer survivors suggested a minimal effect of the low dose arm. As such, Drs. [name] and [name] decided to adapt the study as follows: change the design to be a single-arm feasibility study in which all participants receive the full “high-dose” intervention, decrease the target recruitment goal, and decrease participant burden by removing intensive data collection methods. These modifications will yield valuable information to determine how best to proceed with future diet and physical activity behavioral interventions in this rural population.

Overview of Study Design. The proposed pilot study will recruit 25 Latinos who are residents of the rural Lower Yakima Valley (LYV) with one or more of the following diagnoses based upon self-report: hypertension, diabetes, cardiovascular disease, obesity, or a history of cancer. Recruitment, retention, and data collection procedures will be carried out by Community Health Educator (CHE) study staff. Eligible participants will undergo online baseline assessments over a period of 1-2 weeks. Interested and eligible participants will be sent an online informed consent, HIPPA and medical records release form and baseline questionnaires to complete.

Following the completion of baseline data collection, participants will receive the intervention. All participants will receive a Fitbit device to self-monitor their PA. The intervention will include 6 biweekly 2-hour Zoom-based nutrition, culinary, and physical activity sessions. The sessions will be led by a local chef consultant and CHE, both trained by the study team. Participants will receive eHealth communication meant to motivate healthy diet and improved PA via educational and motivating text messages and using resources available as part of the study-related website over a 3-month period. Following completion of the 3-month intervention period, repeated baseline at-home assessments will take place and an exit intervention completed. The exit interview will include questions regarding acceptability and accessibility of the intervention for participants.

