3.3.1 Primary Endpoints

Accrual rate, adherence (online sessions attendance in intervention arm, text message responses, and use of website), retention (completion of all study assessments), and acceptability (exit interview). Feasibility of intervention delivery for staff within in the rural community context will also be assessed and necessary adaptations from the urban intervention delivery process will be documented.

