13.3 Additional Outcome Measures and Statistical Methods

Demographic and clinical characteristics will be measured via an online questionnaire on demographics, comorbid conditions, medical history, and medication use (baseline only).

Intervention feasibility will be measured by accrual, adherence (attendance to online group sessions, response to text messages, and use of website), acceptability of the interventions (exit interview and motivation interviewing educator interaction, MIMSI), quantitative data collection processes (percent completed and duration of staff assistance to complete surveys), and qualitative (exit interviews) data, and retention at 3 months. MIMSI will be administered prior to the exit interview. Exit interviews will be conducted by *promotoras* and audio- recorded and later transcribed for analyses. Feasibility of intervention delivery for staff within in the

rural community context will also be assessed and necessary adaptations from the urban intervention delivery process will be documented.

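### Does retention, a primary endpoint with no stated denominator and an assessment set cut mid-study, need to be redefined?

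*Combined protocol and SAP*

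**What the plan says.** The synopsis lists the primary endpoints as "Accrual rate, intervention adherence, study retention, data completion rates", followed by acceptability and delivery adaptations, so retention and data completion are separate items. Section 3.3.1 gives "retention (completion of all study assessments" and section 13.2 repeats it: "Retention will be measured by completion of all study assessments". Section 13.3 lists "retention at 3 months" among the feasibility measures. Section 13.2 also refers to "Statistical differences in retention rates for each study assessment between study arms", to be compared by Chi-square, although section 13.1 describes a single-arm study. The same paragraph of 13.2 says that every endpoint is summarised descriptively.

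Section 1.0 reports that in October 2021 "investigation into the reason for slow recruitment (n=22 to date) revealed a high burden of data collection for potential participants". The response was to move to one arm, lower the recruitment goal (now 25) and "decrease participant burden by removing intensive data collection methods". Section 5.0 requires signed consent for registration. Section 6.1 puts consent before a baseline and run-in of up to 8 weeks, whereas the design overview in section 1.0 gives 1-2 weeks for baseline. Table 1 has one follow-up, T2, which section 6.7 places at 3 months. Section 13.3 adds that "MIMSI will be administered prior to the exit interview", but Table 1 does not list MIMSI.

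**The concern.** A primary proportion needs a numerator and a denominator. Here the numerator appears to be worded three ways: all assessments completed, a rate for each assessment, and status at 3 months. The denominator could be those who consented, those who finished the run-in, or those who started the intervention. People can be lost between consent and start, and one stated purpose of the run-in is to see whether participants can complete the assessments.

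The content of the full assessment set also changed with 22 people already recruited. The text does not say whether they count toward the 25 or which set they would be scored on. If they all count, 25 - 22 = 3 places remain for people recruited entirely under the reduced set.

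The results are meant to inform a larger trial, where a retention rate would inflate the enrolment target. If one cohort can yield several retention figures, the choice among them might be made after the data are seen.

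**Working it through.** **Are there three definitions?** Sections 3.3.1 and 13.2 say the same thing. Section 13.3 adds a time point. Table 1 has a single follow-up, at 3 months, so the two combine as completion of all assessments through the 3-month visit. The per-assessment wording occurs only inside the between-arm comparison, which is left over from the two-arm design. That leaves one definition and one obsolete sentence. The per-assessment information is not lost, because data completion is its own primary endpoint in the synopsis and percent completed appears in 13.3.

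**How far could the denominator move the figure?** The plan states no expected retention, precision or threshold, so there is no figure of its own to reproduce. The counts below are assumptions: 25 consent, 22 start, 20 give any 3-month data, 18 complete everything. Rate = x/n with exact (Clopper-Pearson) 95% limits; enrolment per 100 evaluable = 100/rate.

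| Numerator / denominator | Rate | Exact 95% CI | Enrol per 100 evaluable |
|---|---|---|---|
| All complete / consented, 18/25 | 72.0% | 50.6-87.9 | 139 |
| Any 3-month data / consented, 20/25 | 80.0% | 59.3-93.2 | 125 |
| All complete / started, 18/22 | 81.8% | 59.7-94.8 | 122 |
| Any 3-month data / started, 20/22 | 90.9% | 70.8-98.9 | 110 |

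Only the first and third rows use the plan's definition. Between them, the denominator alone moves the rate by 81.8 - 72.0 = 9.8 points. Rows two and four need a looser numerator that the plan does not use. The interval for 18/25 spans 87.9 - 50.6 = 37.3 points, so a study of this size fixes retention only loosely under either denominator. The rows describe the same people, so overlapping intervals do not make the definitions equivalent. They do show how little weight any one figure can bear in planning.

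**Does all versus each matter?** Table 1 marks five items at T2: weight, activity questionnaire, psychosocial and quality of life, knowledge and preferences, and exit interview. If each were completed by an assumed 90%, the all-complete rate would be 0.90^5 = 59.0% under independence. The bounds are 1 - 5 x 0.10 = 50% and, with full overlap, 90%. The gap could be large, but it is the difference between two reported quantities, retention and data completion.

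**The 22 earlier recruits.** The goal was lowered in the same change, so the 22 accrued against an earlier target that the document does not give. Section 1.0 separates recruitment from consenting, and nothing says how many of the 22 had consented, completed baseline or reached 3 months. Anyone among them not yet at 3 months could be followed under the reduced set. Three remaining places therefore does not mean that only three people are assessed that way. Even on the extreme reading, 3/3 retained has a lower 95% limit of 0.025^(1/3) = 29.2%. A before-and-after comparison would show nothing, and none is planned.

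**The case for a change.** The best argument for acting is that wording costs almost nothing and a primary endpoint deserves a written denominator. Consent and forms are already handled in REDCap. Section 6.6 has staff pursue 3-month data even from people who do not fully adhere, so partial completers are foreseeable. They would be retained in the everyday sense but not under the all-assessments rule. Fixing the rule beforehand would also remove any suspicion that it was chosen to flatter the result.

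Part of this stands: the denominator and the scoring of earlier recruits are not written down, and the between-arm sentence should not be there. The remedies that go further are weaker:

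- Counting anyone with any 3-month assessment as retained replaces a definition the protocol states twice with a more lenient preference.
- Scoring people against what was required when they consented would mark someone incomplete on assessments later withdrawn, which creates an artefact.
- The start date in section 12.0 is assigned with a text-message suite, so it is not clearly a record of when the intervention began.
- Section 1.0 ties data-collection burden to slow recruitment of potential participants. That concerns accrual, so whether the reduction improved retention is not a question the study set itself.
- The absence of MIMSI from Table 1 cannot be pressed. Section 6.1 refers to Appendix D for measurement tools and timing, and that appendix is not available here.

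**Conclusion.** The omissions are real but call for no change. The plan has one usable definition of retention, all assessments completed, with its time point. What is unwritten is detail that an analyst reporting a single-arm study of 25 people would supply: a participant flow from consent through start to 3 months, counts beside every percentage, and a note on anyone enrolled before the assessments were reduced. Scoring such people on the items common to both sets is the obvious choice. Losses remain visible in any case, because section 10.2 requires drop-outs and withdrawals to be reported with reasons. The between-arm test is a clerical remnant; it cannot be run with one arm, and removing it alters no result.

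On the assumed counts and the plan's own numerator, the denominator is worth about 10 points (72.0% against 81.8%), inside intervals some 35 to 37 points wide. The true size cannot be known from the documents. The analysis is descriptive with no go/no-go threshold, so no error rate, power or stated decision depends on it. The judgement rests on both counts and denominators being reported. If a single percentage were carried into the later trial's sample size without its denominator, the concern would become real there.
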